## 6.7 Concomitant therapy

All medications administered within 4 weeks prior to the administration of study drugs and all concomitant therapy administered during the study, along with the reasons for therapy, will be recorded.

The investigator should instruct the patient to notify the study site about any new medications he/she takes after the start of the study drug including all over-the-counter medication. All medications (other than study drug) and significant non-drug therapies (including physical therapy and blood transfusions) administered after the patient starts treatment with study drug must be listed on the Concomitant medications/Significant non-drug therapies after start of study drug CRF.

The patients should also be discouraged from taking over-the-counter medications for diarrhea. The use of prescription medication for diarrhea is also to be avoided while patients are receiving study drug treatment, but exceptions may be made if the medication is to treat an adverse event.

The concomitant medication CRF is to be used as an ongoing log, and must be updated as necessary to reflect all medications taken.

The use of anticoagulant medication should be avoided. Patients currently receiving supplemental pancreatic enzymes may be enrolled, but they should not start such treatment or increase the dose while on study.

The use of concomitant medications that might lead to QT prolongation is prohibited and would require the discontinuation of the patient prior to starting the respective QT prolonging medication. Please check <http://www.azcert.org/medical-pros/drug-lists/browse-drug-list.cfm> for a list of QT prolonging drugs.

## 6.8 Study drug discontinuation

Study drug must be discontinued and the subject withdrawn from the trial if the investigator determines that continuing would result in significant safety risk for that subject. The following circumstances require study drug discontinuation:

Pregnancy

The occurrence of an adverse event or of a clinically significant laboratory change or abnormality that, in the judgment of the investigator, warrants discontinuation of treatment.

Subjects who have fasting plasma glucose > 240 mg/dL confirmed by repeat measurement

Any CTC grade 3 or higher abnormalities in hematology or chemistry parameters judged clinically significant by the Investigator

Any confirmed QTcF > 500 ms or confirmed increase of QTcF > 60 ms from baseline

ALT or AST > 3x ULN and Total Bilirubin  $\geq$  2 x ULN and ALP > 2 x ULN

ALT or AST > 5x ULN and  $\leq$  8 x ULN persistent for more than 2 weeks

ALT or AST > 8 x ULN

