### 5.2.2 Exclusion criteria

Patients will be considered ineligible for this study if they meet any of the following criteria:

Patients with a known hypersensitivity to SST analogs or any component of the pasireotide LAR or SQ formulations.

Patients with known malabsorption syndrome, short bowel or chologenic diarrhea not controlled by specific therapeutic means.

Patients with abnormal coagulation (PT or a PTT elevated by 30% above normal limits).

Patients on continuous anticoagulation therapy. Patients who were on anticoagulant therapy must complete a washout period of at least 10 days and have confirmed normal coagulation parameters before study inclusion.

Patients with symptomatic cholelithiasis.

Patients who are not biochemically euthyroid.

Patients with known history of hypothyroidism are eligible if they are on adequate and stable replacement thyroid hormone therapy for at least 3 months.

Serum magnesium  $\geq$  ULN

QT-related exclusion criteria:

QTcF at screening  $>$  470 msec

Patients with a history of syncope or family history of idiopathic sudden death

Patients who have sustained or clinically significant cardiac arrhythmias

Risk factors for Torsades de Pointes such as hypokalemia, hypomagnesemia, cardiac failure, clinically significant/symptomatic bradycardia, or high-grade AV block

Patients with concomitant disease(s) that could prolong QT such as autonomic neuropathy (caused by diabetes, or Parkinson's disease), HIV, cirrhosis, uncontrolled hypothyroidism or cardiac failure

Family history of long QT syndrome

Concomitant medications known to prolong the QT interval.

Potassium  $<$  or  $=$  to 3.5

Patients who have any severe and/or uncontrolled medical conditions or other conditions that could affect their participation in the study such as:

Patients who have Uncontrolled diabetes as defined by HbA1c $>$ 8%\* despite adequate therapy

Patients with the presence of active or suspected acute or chronic uncontrolled infection or with a history of immunodeficiency, including a positive HIV test result (ELISA and Western blot). An HIV test will not be required; however, previous medical history will be reviewed.

Non-malignant medical illnesses that are uncontrolled or whose control may be jeopardized by the treatment with this study treatment.

Liver disease such as cirrhosis, decompensated liver disease, chronic active hepatitis or chronic persistent hepatitis.

Baseline ALT or AST  $>$ 3x ULN

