**Pancreatic****Pancreatitis**

Grade 1	Maintain dose level
---------	---------------------

Grade 2	Maintain dose level
Grade 3	Omit dose and discontinue patient from study treatment
Grade 4	Omit dose and discontinue patient from study treatment
Amylase and/or lipase	
Grade 1 (> ULN - 1.5 x ULN)	Maintain dose level
Grade 2 (> 1.5 - 2.0 x ULN)	Maintain dose level
Grade 3 (> 2.0 - 5.0 x ULN)	For asymptomatic: Omit dose until resolved to ≤ Grade 1, then 
 
• If resolved ≤ 7 days, then maintain dose level
 
• If resolved > 7 days, then ↓ 1 dose level
 
 For symptomatic: Omit dose and discontinue patient from study treatment
Grade 4 (> 5.0 x ULN)	Omit dose and discontinue patient from study treatment A CT scan or other imaging study to assess the pancreas, liver and gallbladder must be performed within 1 week of the first occurrence of any ≥ CTCAE grade 3 of amylase and/or lipase.
Endocrine/metabolic	
Fasting plasma glucose (FPG) or 2-hour postprandial capillary glucose (PPG)	
FPG <126 mg/dL or PPG < 140 mg/dL	Maintain dose level
Grade 1 (> ULN – 160 mg/dL)	appendix 2 section 12.2.
Grade 2 (> 160 – 250 mg/dL)	appendix 2 section 12.2.
Grade 3 (> 250 – 500 mg/dL)	appendix 2 section 12.2.
Grade 4 (> 500 mg/dL)	appendix 2 section 12.2.
Cardiac	
Cardiac - prolonged QTc interval	

 
• QTcF > 480 ms and ≤ 500 ms
 
• QTcF > 500 msec
 
	
If at any time a QTcF > 480 ms and ≤ 500 ms is observed a cardiology consultation must be sought to re-evaluate the abnormal ECG finding.
 
 
1. Triplicate ECGs (2-3 minutes apart) need to be taken approximately 1 hour after the initial ECG.
 
2. If the mean QTcF is > 500 ms, the patient must postpone study treatment until a cardiologist has re-evaluated the ECG.
 
3. The re-evaluation of ECG needs to be done as soon as practical but within 7 days of the initial abnormal ECG.
 
4. If the cardiologist confirms a mean QTcF > 500 ms, the patient must be discontinued.
 

Cardiac general	
Grade 1 or 2	Maintain dose level
Grade 3	Omit dose until resolved to ≤ Grade 1, then ↓ 1 dose level
Grade 4	Omit dose and discontinue patient from study treatment
Other adverse events	
Grade 1 or 2	Maintain dose level
Grade 3	Omit dose until resolved to ≤ Grade 1, then ↓ 1 dose level

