## 6.10 Overall Study Stopping Rules

Stopping criteria for hyperglycemia and other side effects, e.g. related to changes in hematology, chemistry, or cardiac test values are **listed in section 6.8**. Pasireotide has already demonstrated acceptable tolerability and efficacy in several completed or ongoing clinical trials (**page 38 Investigator Brochure**) and the LAR formulation is being examined in a phase 3 study for treatment of Acromegaly NCT00600886; Novartis data on file, and for Cushing disease (sc formulation; CSOM230B2305] recently reported (Colao, Petersenn et al. 2012). In the latter study hyperglycemia-related adverse events occurred in 73% of patients necessitating 6% discontinuing study treatment Plasma glucose levels increased 10% from baseline compared with a 2% increase in placebo ( $P<0.02$ ) after commencing octreotide treatment and no patient developed diabetes in our prior somatostatin analog study using OctLAR.

Gastrointestinal problems are the most commonly reported AEs associated with the use of SOM230, (predominantly mild diarrhea grade 1 or 2, and nausea requiring no treatment or study discontinuation). In our prior somatostatin analog study in PKD, only 1/42 individuals discontinued that study after one year (due to steatorrhea) and none discontinued because they developed diabetes. Based on our prior experience and others' studies of tolerability and side effects associated with OctLAR (and also with lanreotide in PKD and PLD), we do not anticipate there will be patient discontinuation >15%, since both drugs have a similar tolerability profile (**Investigator brochure section 6.2**). Hence, we do not anticipate we will need to stop this study in this patient population due to lack of study power. If there is no efficacy found after the first year analysis is complete then we will terminate the open label extension. We will be monitoring each patient closely (**table 8**) for expected and unexpected drug side effects. If there are any

serious suspected adverse reactions (>1) that were unexpected these would be evaluated by the sponsor-investigator and the risk/benefit of study continuation would be analyzed. Novartis also reserves the right to stop the study (**section 13.1.3**).

- Colao, A., S. Petersenn, et al. (2012). "A 12-Month Phase 3 Study of Pasireotide in Cushing's Disease." New England Journal of Medicine **366**(10): 914-924.

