#### 7.5.4.8 Electrocardiogram (ECG)

A 12-lead electrocardiogram (ECG) and rhythm strip will be performed at baseline and 30 minutes after the first dose one half and 3 monthly for the first year and every 6 months in year 2. Repeat ECG on the 21st day after the injection, then every 3 months thereafter.

If a clinically significant abnormality is detected, the electrocardiogram will be repeated at the discretion of the Investigator until the abnormality has been resolved. *A cardiology consultation must be sought as soon as practical but within 7 days of the initial abnormal ECG and the cardiologist must re-evaluate the ECG (this can be done by the central cardiologist). An echocardiogram may also be required.*

- If a QTcF > 480msec is NOT confirmed, no further action needs to be taken.
- If a QTcF > 480msec is confirmed, a cardiologist must perform a thorough examination (such as reviewing baseline ECG, concurrent medications and performing a cardiovascular examination, including at least a cardiac auscultation) to assess the patient for cardiovascular risk factors.

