- If following the examination by the cardiologist, the investigator considers that there is not an acute cardiovascular safety risk and that the patient could continue to receive study medication, a Holter ECG (24hr or 48hr depending on the study) must be recorded soon as practical but within 7 days after the initial abnormal ECG / at the next pasireotide/octreotide LAR injection (for studies using LAR). The Holter-ECG must be started 30min prior to an injection of study medication.

The results of the ECGs, cardiac examination, Holter-ECGs and the recommendation by the cardiologist must be evaluated by the investigator to determine whether the patient should continue in the trial or not (discontinuation criteria to be followed).

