#### **QT-related discontinuation criteria**

- Confirmed  $\text{QTcF} > 480\text{msec}$  and discontinuation recommended by a cardiologist
- Mean  $\text{QTcF} > 500\text{ msec}$  measured by triplicate ECGs
- Significant arrhythmia findings from Holter monitoring such as:
  1. Any ventricular or supra-ventricular tachyarrhythmia associated with symptoms of hemodynamic compromise
  2. Sustained ventricular tachycardia (>30 sec) irrespective of symptoms
  3. Recurrent non-sustained VT ( $\geq 3$  beats) during any 24-hour monitoring period
  4. Torsades de Pointes (TdP)
  5. Cardiac arrest
  6. Pause >5 seconds
  7. Second or third degree AV block
- New occurrence of clinically significant/symptomatic bradycardia
- Increased risk of QT prolongation by use of QT prolonging medication
- Hypokalemia (<3.5 mmol/L) or hypomagnesaemia (<0.7 mmol/L) confirmed by repeat testing that is either a new finding or accompanied by vomiting or diarrhea and not corrected by treatment

[figure not shown]

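### The mandatory stop for a confirmed QTcF rise above 60 ms appears only in Section 6.8; Table 7, Section 7.5.4.8 and Appendix 3 omit it, and Appendix 3 can keep such a patient on drug

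*Combined protocol and SAP*

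**What the plan says.** Section 6.8 gives a list of circumstances in which study drug has to be discontinued. Its QT entry reads "Any confirmed QTcF > 500 ms or confirmed increase of QTcF > 60 ms from baseline". The two conditions are joined by *or*, so the second alone, a "confirmed increase of QTcF > 60 ms from baseline", is enough. Unlike the adverse-event and grade 3 laboratory entries in the same list, this entry is not qualified by investigator judgement. Section 6.10 refers back to it: "Stopping criteria for hyperglycemia and other side effects, e.g. related to changes in hematology, chemistry, or cardiac test values are" found in Section 6.8.

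Three other places tell staff what to do with a long QTcF:

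- **Table 7 (Section 6.6), cardiac QTc row.** If a value above 480 and up to 500 ms "is observed a cardiology consultation must be sought to re-evaluate the abnormal ECG finding". Triplicate ECGs follow. Discontinuation is required only when a cardiologist confirms a mean above 500 ms.
- **Section 7.5.4.8.** The only numeric limit is 480 ms. If a value above 480 ms "is NOT confirmed, no further action needs to be taken". If it is confirmed, a cardiologist examines the patient.
- **Appendix 3 (Section 12.3).** For a confirmed value above 480 and up to 500 ms, if the investigator sees no acute cardiovascular risk and considers that "the patient could continue to receive study medication, a Holter ECG" is recorded. The list of QT discontinuation criteria at the end of the appendix includes a confirmed value above 480 ms "and discontinuation recommended by a cardiologist", and a triplicate mean above 500 ms. It also covers Holter arrhythmias, bradycardia, QT-prolonging drugs and low potassium or magnesium. It contains no change-from-baseline criterion.

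Section 5.2.2 excludes patients whose "QTcF at screening" is above 470 msec.

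**The concern.** The same ECG can lead to two different instructions. Section 6.8 makes the rise from baseline a mandatory stop. The texts that staff would have open when managing a long QTcF do not mention a rise from baseline, and one of them provides a route to further dosing. The closing note of Table 7 sends the reader to the appendices for QT guidance, not to Section 6.8, and Appendix 3 does not refer back to Section 6.8.

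What is at stake is patient safety and consistent handling. Section 1.5.1 reports a peak QTcF effect of 17.5 ms versus placebo for subcutaneous pasireotide at 1950 µg b.i.d. in healthy volunteers. That is a different formulation and regimen, but it shows that a QT effect is known. A stopping rule missing from the QT guideline may be missed, or applied to some patients and not to others.

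**Working it through.** There is no planned figure to reproduce. The check compares the texts and applies threshold arithmetic.

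**Inputs**

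- Section 6.8: stop if confirmed QTcF > 500 ms, or if confirmed QTcF − baseline > 60 ms.
- Table 7 and Appendix 3: absolute limits of 480 and 500 ms. Section 7.5.4.8: absolute limit of 480 ms.
- Section 5.2.2: screening QTcF at most 470 ms. Baseline is assumed here to lie under the same ceiling.

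**When can a rise above 60 ms stay below the absolute limits?**

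Let *b* be the baseline. The on-drug value exceeds *b* + 60.

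- It can end at or below 500 ms only if *b* < 500 − 60 = 440 ms.
- It can end at or below 480 ms only if *b* < 480 − 60 = 420 ms.
- For *b* from 440 to 470 ms it always ends above 440 + 60 = 500 ms, so the absolute rule already covers it.

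**Texts side by side, all readings confirmed**

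| Example | Rise | Section 6.8 | Table 7 | Section 7.5.4.8 | Appendix 3 |
|---|---|---|---|---|---|
| 425 to 490 ms | 490 − 425 = 65 ms | Stop | Cardiology consultation, triplicate ECGs | Cardiology examination | Stop if the cardiologist recommends it or the investigator sees acute risk; otherwise continue with Holter |
| 400 to 465 ms | 465 − 400 = 65 ms | Stop | Nothing triggered | Repeat ECG and consultation only if judged clinically significant | Nothing triggered |
| Baseline 440 ms or more | above 60 ms | Stop | Stop (confirmed mean above 500 ms) | No 500 ms rule; cardiology examination | Stop (mean above 500 ms) |

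The first row is a direct conflict: one text requires stopping and another leaves it to judgement for the same patient. The second row is an omission: Section 6.8 applies, but nothing in Table 7 or Appendix 3 leads staff to it.

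**The sentence that closes the work-up.** In Section 7.5.4.8 and Appendix 3, the statement that nothing more is needed most naturally applies to a reading first seen above 480 ms and not confirmed. Even so, it can conflict with Section 6.8. If the baseline is 410 ms and a first reading above 480 ms is re-read at 475 ms, the rise is 475 − 410 = 65 ms. The sentence ends the work-up, while Section 6.8 requires stopping if the 475 ms value is taken as confirmed.

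**The case against.** The strongest reply is that the rules are cumulative. Section 6.8 is mandatory and Section 6.10 points to it, whereas Table 7 is headed as recommended modifications and its footnote calls the appendices guidance. On that reading a patient stops if any criterion is met. Both Appendix 3 branches also carry a reminder that discontinuation criteria apply, and the section titled for study drug discontinuation is 6.8. This supports treating Section 6.8 as controlling. It does not remove the conflict: the reminder names no section, and the only list headed as QT discontinuation criteria is in the same appendix, omits the rise, and makes stopping above 480 ms depend on the cardiologist.

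Other points, and what stands of them:

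- **At or below 480 ms the other texts are silent rather than contradictory.** This is correct, and that case is presented here as an omission.
- **The cardiologist reviews the baseline ECG.** This happens only after a value above 480 ms is confirmed, and no numeric change is attached to the review.
- **A figure after the Appendix 3 list is not visible.** The finding therefore concerns the written text. Whatever the figure shows, the written list, Table 7 and Section 7.5.4.8 still lack the criterion.
- **The 470 ms ceiling is set at screening.** Table 8 also marks an ECG at randomization and Table 9 asks for one before the first dose, with no ceiling stated for either. Applying 470 ms to baseline is an assumption. The 440 and 420 ms cut-offs do not depend on it.
- **No frequency is shown.** This is correct, and none is claimed.

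**Conclusion.** The concern holds. The 60 ms criterion appears in the visible text only in Section 6.8. For a baseline below 440 ms, a confirmed rise above 60 ms that ends above 480 and at or below 500 ms is a mandatory stop in Section 6.8 and a matter of judgement in Appendix 3. For a baseline below 420 ms, the rise can also end at or below 480 ms, where Table 7 and Appendix 3 trigger nothing. For baselines of 440 ms and above, Section 6.8, Table 7 and Appendix 3 all lead to stopping.

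The conclusion rests on the written text and on the reader of Appendix 3 using that appendix's own list. How many patients would be affected cannot be estimated from the documents. No effect on power or on the month-12 analysis set is claimed. The correction should be made because it concerns a safety stopping rule.

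**What to change.** Keep Section 6.8 as the controlling list, as Section 6.10 already implies, and align the other texts with it:

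1. Add discontinuation for a confirmed QTcF rise of more than 60 ms over baseline to the QTc row of Table 7, to Section 7.5.4.8 and to the Appendix 3 list, or have each state that the QT criteria of Section 6.8 apply.
2. In Appendix 3, make the Holter continuation path available only when no Section 6.8 QT criterion is met, and name Section 6.8 where the text now refers to unspecified discontinuation criteria.
3. In Section 7.5.4.8 and Appendix 3, limit the sentence that ends the work-up to cases where no other Section 6.8 QT criterion is met.

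The cost is wording only. No visit, ECG or analysis is added.

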**Hepatic See also section 7.5.4.1****Bilirubin**

Grade 1 (< 2 x baseline value)	Maintain dose level
Grade 2 (2-3 x baseline value)	Omit dose until resolved to ≤ Grade 1, then 
 
• If resolved ≤ 7 days, then maintain dose level
 
• If resolved > 7 days, then ↓ 1 dose level
 

Grade 3 (> 3.0 - 10.0 x ULN)	Omit dose until resolved to ≤ Grade 1, then 
 
• If resolved ≤ 7 days, then maintain dose level
 
• If resolved > 7 days, then ↓ 1 dose level
 

Grade 4 (> 10.0 x ULN)	Omit dose and discontinue patient from study treatment

NOTE: If grade 3 or 4 hyperbilirubinemia is due to the indirect (unconjugated) component only, and hemolysis as the etiology has been ruled out as per institutional guidelines (e.g. review of peripheral blood smear and haptoglobin determination), then ↓ 1 dose level and continue treatment at the discretion of the investigator

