**AST or ALT**

Grade 1 (> ULN - 2.5 x ULN)	Maintain dose level
Grade 2 (> 2.5 - 5.0 x ULN)	Maintain dose level
Grade 3 (> 5.0 and ≤ 8x ULN)	For ALT or AST > 5x ULN and ≤ 8x ULN: 
 
• Study medication should be temporarily interrupted & liver chemistry monitored every 3-4days until resolution or return to baseline.
 
• If resolution or return to baseline does not occur after 2 weeks, the patient should be discontinued.
 
• If ALT or AST returns to less than 5x ULN, study drug can be resumed and patient can continue study per protocol
 
• If ALT or AST rises above 5x ULN anytime after study drug is resumed, then study drug should be discontinued immediately.
 

Grade 4 (> 20.0 x ULN)	Omit dose and discontinue patient from study treatment

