#### **7.5.4.1 Abnormal liver function management:**

Perform within 72 hours of awareness of abnormal LFTs:

Perform liver-directed medical history and physical examination (i.e. assess occupational hazards, concomitant medications including OTC meds, intercurrent illness, etc)

Liver chemistry tests: ALT, AST, total bilirubin, (fractionate to direct/indirect bilirubin if total bilirubin is > 2.0x ULN), Alb, PT (INR), ALP, and GGT

Perform hepatitis screen: anti-HAV, IgM (to confirm acute hepatitis A), HbsAg, Anti-HBc, anti-HCV (if positive PCR viral load should be assessed), Anti-HEV, ANA antibodies, anti-smooth muscle anti-bodies, CMV, EBV

Perform abdominal ultrasound (liver and biliary tree)

Liver chemistry tests should be monitored every 3-4 days for LAR studies until resolution or return to baseline status.

For ALT or AST > 5x ULN and ≤ 8x ULN:

- Study medication should be temporarily interrupted and liver chemistry tests monitored **every 3-4 days** until resolution or return to baseline
- If resolution or return to baseline does not occur after 2 weeks, the patient should be discontinued.
- If ALT or AST returns to less than 5x ULN, study drug can be resumed and patient can continue study per protocol
- If ALT or AST rises above 5x ULN anytime after study drug is resumed, then study drug should be discontinued immediately.

Resolution return to baseline does not occur after two weeks the patient should be discontinued

If ALT or AST rises about 5X ULN anytime after study drugs resumed and study drug to be discontinued immediately

Study medication should be discontinued immediately if any of the discontinuation criteria below are met: (see appendix 4)

ALT or AST > 3x ULN and Total Bilirubin ≥ 2x ULN and ALP < 2x ULN

ALT or AST > 5x ULN and ≤ 8x ULN persistent for more than 2 weeks

ALT or AST > 8x ULN

Re-challenge of study medication is prohibited once discontinuation criteria are met.

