## 12.4 Appendix 4 SOM230 LFT Management Algorithm (s.c. and LAR Studies)

### Revised SOM230 Abnormal liver function discontinuation criteria:

Hepatic-related discontinuation criteria for all ongoing studies
Study medication should be discontinued immediately if any of the discontinuation criteria below are met:

 
ALT or AST > 3x ULN and Total Bilirubin ≥ 2x ULN and ALP < 2x ULN
 
ALT or AST > 5x ULN and ≤ 8x ULN persistent for more than 2 weeks
 
ALT or AST > 8x ULN
 

Re-challenge of study medication is prohibited once discontinuation criteria are met.

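### Section 6.8 states the combined hepatic stopping rule with ALP above 2x ULN, the reverse of section 7.5.4.1 and Appendix 4, so the list that section 6.10 cites misses patients whom the other two stop permanently

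*Combined protocol and SAP*

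**What the plan says.** Three current sections state a combined hepatic rule for stopping study drug.

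- **Section 6.8** lists circumstances in which discontinuation is mandatory. Its combined rule is ALT or AST above 3x ULN, with total bilirubin at least "2 x ULN and ALP > 2 x ULN".
- **Section 7.5.4.1** requires immediate discontinuation for "ALT or AST > 3x ULN and Total Bilirubin ≥ 2x ULN and ALP < 2x ULN". It adds: "Re-challenge of study medication is prohibited once discontinuation criteria are met".
- **Appendix 4 (section 12.4)**, under the heading "Revised SOM230 Abnormal liver function discontinuation criteria", repeats the 7.5.4.1 version, including the bar on re-challenge.

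The other two hepatic criteria agree in all three places: transaminases above 5x and up to 8x ULN for more than two weeks, and transaminases above 8x ULN.

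The cross-references point in different directions. Section 6.10 says that the stopping criteria, including those for chemistry values, are "listed in section 6.8". The liver block of Table 7 is marked "Hepatic See also section 7.5.4.1". The liver-test instructions placed just before section 1.5.2.2 name Appendix 4 as the management algorithm.

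**The concern.** The ALP condition decides which patients the combined rule catches, and 6.8 has it the opposite way round from the other two sections. The section whose title and cross-reference make it the obvious place to look therefore selects a different, non-overlapping group of patients.

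This matters most for transaminases above 3x and up to 5x ULN. In that band the combined rule is the only numeric transaminase-based mandatory stop in 6.8. If its sign is wrong, a patient whom Appendix 4 bars from further drug can be kept on treatment by someone working from 6.8. An injection given in error cannot be withdrawn: section 1.5.1.1.1 describes slow release for up to 42 days after a single dose.

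**Working it through.** There is no sample size, power or alpha figure to reproduce. The check sets the rules side by side as logical conditions and runs laboratory profiles through them.

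**Inputs** (all values in multiples of ULN unless stated)

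- Combined rule in 6.8: ALT/AST > 3, bilirubin ≥ 2, ALP > 2.
- Combined rule in 7.5.4.1 and Appendix 4: ALT/AST > 3, bilirubin ≥ 2, ALP < 2.
- Shared criteria: ALT/AST > 8; or > 5 and ≤ 8 for more than two weeks.
- Entry limits in 5.2.1: bilirubin ≤ 1.5, ALP ≤ 2.5.
- Table 7, bilirubin: "Grade 1 (< 2 x baseline value") means maintain the dose; 2 to 3 times baseline means omit until resolved, then resume; grade 3 starts above 3x ULN.
- Table 7, AST or ALT: "Grade 2 (> 2.5 - 5.0 x ULN") means maintain the dose; grade 3 starts above 5x ULN.

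**Step 1: can both versions apply to one patient?** No. ALP > 2 and ALP < 2 exclude each other, and ALP = 2 satisfies neither.

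**Step 2: three profiles**

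| Case | ALT | Bilirubin | ALP | 6.8 combined rule | 7.5.4.1 / Appendix 4 |
|---|---|---|---|---|---|
| A | 4 | 2.5 | 1.0 | not met | met: stop, no re-challenge |
| B | 4 | 2.5 | 2.3 | met: stop | not met |
| C | 4 | 2.5 | 2.0 | not met | not met |

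Case B is compatible with entry, since 5.2.1 admits ALP up to 2.5x ULN.

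**Step 3: where do the full hepatic lists disagree?** Adding the shared criteria removes the disagreement when ALT/AST is above 8, or above 5 and up to 8 for more than two weeks. Leaving aside ALP of exactly 2, which meets neither combined rule, the lists still disagree when bilirubin is at least 2 and ALT/AST is either above 3 and up to 5, or above 5 and up to 8 without lasting beyond two weeks.

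**Step 4: does anything else in 6.8 catch case A?** Not by number. ALT 4 is below the 5x and 8x criteria. It is also below Table 7's grade 3 limit for transaminases (> 5), and bilirubin 2.5 is below the grade 3 limit for bilirubin (> 3), so on those limits the clause on grade 3 or higher abnormalities does not reach this patient. Only the investigator-judgement items remain.

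**Step 5: do the single-parameter rows of Table 7 close the gap for case A?**

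- ALT 4 is grade 2: maintain the dose.
- Bilirubin 2.5 with baseline 1.5 is 2.5 / 1.5 = 1.67 times baseline: grade 1, maintain the dose.
- Bilirubin 2.5 with baseline 1.0 is 2.5 / 1.0 = 2.5 times baseline: grade 2, omit and later resume.
- With baseline 1.5, the maintain row runs up to just under 2 × 1.5 = 3.0x ULN, so any bilirubin from 2x to just under 3x ULN falls in it.
- At bilirubin 2.5, the maintain row applies for any baseline above 2.5 / 2 = 1.25x ULN.

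In no case do these rows produce the permanent stop that 7.5.4.1 and Appendix 4 require.

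**Step 6: after correction.** With ALP < 2 in 6.8, its three hepatic criteria match the other two sections line for line and no discordant profile remains.

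**The case against.** The strongest reply is that the lists add to each other. Nothing in 6.8 says that it is exhaustive, and 7.5.4.1 is mandatory in its own right, so case A must stop whatever 6.8 says. Applied together, the sections stop both ALP groups except at exactly 2x ULN. The hepatic pointers (Table 7, and the liver-test text before 1.5.2.2) lead to the version with ALP below 2x. The 72-hour work-up in 7.5.4.1 brings the reader to that version, and the Day 22 and Day 50 liver tests must be assessed before the next injection. The maintain-dose illustration needs baseline bilirubin above 1.25x ULN. Finally, reversing the sign removes a numeric stop in 6.8 for patients with ALP above 2x, some of whom may enter with such values; over-stopping them errs on the safe side.

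Much of this stands as mitigation. A reader who consults every section would stop case A, and the safeguards reduce the chance of harm. The pointers also support below 2x as the intended direction. They do not make 6.8 correct: no section says that the lists are to be combined or which prevails, and 6.10 sends the reader to 6.8 alone. Combining them would also enforce a stop for ALP above 2x that the revised criteria do not contain. The point about raised ALP at entry is sound and is a decision for the fix. A misread symbol in the PDF text cannot be fully excluded, but the surrounding symbols in 6.8 read sensibly, and checking the source document would settle it.

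**Conclusion.** The concern holds. Section 6.8 is wrong as written, or the other two sections are; they cannot all be right. The weight of the text favours ALP below 2x ULN: two sections state it, one of them is labelled as revised, and Table 7 refers hepatic events to it.

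The contradiction is confined to bilirubin of at least 2x ULN with transaminases above 3x and up to 8x ULN, excluding those above 5x that last more than two weeks. Within that region the two rules give opposite instructions on either side of ALP 2x ULN, and neither gives one at exactly 2x. How many patients would fall there cannot be estimated from the documents. The case for correction rests on a mandatory safety threshold being stated in opposite directions, and it must be fixed. It assumes that the sign in 6.8 was extracted correctly and that 6.8 may be read without 7.5.4.1, as 6.10 invites.

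**What to change.** 1. In 6.8, change the ALP condition of the combined rule to below 2x ULN and add that re-challenge is prohibited, or cross-refer to Appendix 4. The sponsor's medical team should confirm the direction first.
2. State how ALP of exactly 2x ULN is handled.
3. State whether patients who enter with ALP between 2x and 2.5x ULN are covered. While their ALP stays above 2x they cannot meet the corrected rule, so the loss of a numeric stop for them in 6.8 should be a deliberate choice.
4. State in Table 7 that the discontinuation criteria in 7.5.4.1 override its single-parameter rows.
5. As a minor tidy-up, replace the Table 7 transaminase row that starts above 20x ULN with one that discontinues above 8x ULN without re-challenge, since 6.8, 7.5.4.1 and Appendix 4 already require stopping there.

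The cost is a short protocol amendment: one sign and the re-challenge wording in 6.8, brief text on the boundary and on entry ALP, and one row plus one line in Table 7. It adds no procedures, visits or patients, though items 2 and 3 need a clinical decision.
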